**Table2.2 Miniscrew Implantation in palate**

Author name	Imaging evaluation	Results
Antonino Lo Giudice et al (2020)	CBCT	A case report about Maxillary Skeletal Expander (MSE)
Vincenzo Ronsivalle et al (2023)	intra-oral scan (IOS) and CBCT scans of each guide were generated were imported into Blue Sky Plan* (USA)	A certain amount of clinical deviation can occur between planned and achieved position of orthodontic miniscrews in the anterior palate.
Giorgio Iodice et al (2010)	models were scanned using a 3D model scanner	Both direct and 3D-assisted TAD insertion methods are safe and accurate in the anterior palate. However, the use of insertion guides could facilitate TAD insertion, providing the opportunity to use palatal implants to the less-experienced clinicians.
Michele Cassetta et al. (2019)	CBCT and dental digital model images	Miniscrew-supported distal jet appliance can be used safely for first upper molar distalization.
Daniele Cantarella et al (2020)	the digital model of dental arches and cone-beam computed tomography (CBCT).	In the present case report, the digital planning was associated with a positive outcome of maxillary expansion and protraction in safety conditions

M. Cassetta, et al. (2018)	the fusion of cone-beam computed tomography (CBCT) and digital dental model images	The present surgical guide allows a controlled and accurate palatal miniscrew placement in three dimensions.
Diego Sánchez- Riofrío et al. (2020)	CBCT	Digital models, CBCT and CAD/CAM technology, are essential to accomplish the goals proposed in this article.
Kristian Kniha et al. (2021)	Preoperative lateral cephalograms; postoperative CBCT	The accuracy of an OMI position can be significantly increased by using a guide extension over the teeth. Vertical implant positions presented the lowest deviations. Postoperative oral scans and CBCTs represent diverging accuracy measurements when compared with virtual planning
Jae-Jung Yua et al. (2012)	CBCT	The accuracy of an OMI position can be significantly increased by using a guide extension over the teeth. Vertical implant positions presented the lowest deviations. Postoperative oral scans and CBCTs represent diverging accuracy measurements when compared with

		virtual planning.
Maria R.et al. (2023)	CBCT and Intraoral scans images	The 3D-printed SGs did not reach the accuracy of the conventional SGs made of Pattern Resin but may provide sufficient accuracy for palatal OMI placement.
Silvia Izabella Pop.et al. (2022)	CBCT	
1. Disinfection with 4% Gigasept (Gigasept Instru AF; Schülke & Mayer GmbH, Norderstedt, Germany) is suitable both for SLA- and DLP-printed surgical guides.
 
2. Heat sterilization at both 121 °C and 134 °C modifies the mechanical properties of the surgical guides and is not recommended as a sterilization method for surgical guides intended for mini-implant placement.

Jian-Hong YU.et al. (2018)	CBCT	Using FE analysis for biomechanical evaluation and combining with CT image, image superimposed method and CAD technique can fabricate accuracy/security customized surgical template for mini-screws with better primary

		stability.
Lucia Pozzan .et al. (2022)	CBCT	
1. All operative steps contribute to a certain degree of deviations that lead to a cumulative effect.
 
2. The laboratory step has a smaller influence on the angular deviations between planned and inserted miniscrews than the clinical steps.
 
3. Cases with 2 TADs can be successfully performed with a 1-visit protocol must be approached with caution, given the lower degree of tolerance of the system.

**Table 2.3. Miniscrew Implantation in infrzygomatic crest zone**

Author name	Imaging evaluation	Results
[name] et al (2022)	the digital model of dental arches and cone-beam computed tomography (CBCT).	In the vertical direction, the accuracy of implantation with the template is higher than that of the traditional method without the template to avoid piercing the maxillary sinus mucosa in the infrzygomatic crest zone

## **2.2 Miniscrew guide**

### **2.2.1 The advantage of Mini-implant guide**

Mini-implant were placed more accurately when using surgical guides than when using a conventional method (Bae MJ et al.,2013). The accurate insertion of mini-implant using the guide allows doctors to precisely transfer the radiographic information from preoperative design to the surgical, thus minimizing the risks of root and injury (Suzuki EY et al.,2008). This novel approach is also leading to short orthodontic treatment time, minimal discomfort, and great patient acceptance.

### **2.2.2 The disadvantage of Miniscrew guide**

The use of guide plates can easily lead to greater economic costs. It is always lead to the additional biological cost such as CBCT. We also need to consider the complications such as the breakage of the surgical guide itself during its use (Lo Giudice A et al.,2021)

### **2.2.3 The design of Miniscrew guide**

The most common currently is the palatal mini-implant guide. As described in Figure 1, the surgical guide has designed some holes aimed at the correct positioning control(Cassetta M et al.,2013).As described in Figure 2, the surgical guide is made of archwire(Pithon MM et al.,2010).As described in Figure 3, the 3D surgical guide

can connect to any desired position by the archwire (Suzuki EY et al.,2008).As described in Figure 4,mini-screw spin-off slots were designed on the surgical template(Yu JH et al.,2018).As described in Figure 5,templates fabricated by SLA bonded with guided sleeves in the trajectory (Liu H et al,2010).

[figure not shown]

Figure 2.2.1 Palatal mini-implant guide

Figure 2.2.2 Guide made of archwire

[figure not shown]

Figure 2.2.3 Guide made of archwire

[figure not shown]

Figure 2.2.4 Guide with mini-screw spin-off slots

[figure not shown]

Figure 2.2.5 Guide with sleeves

## 2.3 Approaches to Improve the safety and stability of Miniscrew

### 2.3.1 Imaging technology

After the 1990s, the application of digital 3D modeling of teeth and jaws in dentistry has become increasingly widespread.

Researchers have developed three-dimensional (3D) scanning techniques to capture the geometry and texture of oral structures, including teeth, gums, and surrounding

tissues. These digital scans are then processed and converted into accurate and detailed virtual models, providing an alternative to traditional plaster models.

Digital oral models offer several advantages over traditional models. Firstly, they enable enhanced visualization and analysis of dental structures, allowing for improved treatment planning and evaluation. Dentists can manipulate the digital models, measure distances, angles, and volumes, and simulate treatment outcomes.

In addition, digital models facilitate communication and collaboration among dental professionals. They can be easily shared, stored, and accessed remotely, enabling interdisciplinary consultations and efficient treatment coordination.

Moreover, digital oral models serve as a valuable resource for dental research and education. Researchers can use these models to study various dental conditions, simulate treatment interventions, and investigate the efficacy of different procedures. Dental students can also enhance their learning experience by practicing virtual procedures on these models.

Despite these advancements, challenges remain in the adoption of digital oral models. Standardization, interoperability, and data security are areas that require further attention. Additionally, the cost of acquiring and maintaining the necessary technologies may limit widespread implementation.

### **2.3.2 Miniscrew guide**

In recent years, with the rapid development of digitalization in oral applications, more accurate research methods have been provided for clinical doctors (Bae MJ et

al,2013). Qiu Lingling reconstructed teeth and jawbone models using CBCT, determined the three-dimensional spatial position of the tooth root using software such as Minics, designed the implantation position and angle, successfully printed resin guide plates, and implanted implant screws (Qiu L et al,2012) . Lo et al.used CBCT for digital design and printing of maxillary implant nail assisted arch expansion devices, and achieved good clinical treatment results(Lo et al,2020). This project successfully combines CBCT and 3Shape intraoral scanning data, uses software to establish an accurate three-dimensional integrated dental model, accurately evaluates the three-dimensional spatial position relationship of teeth, designs personalized micro implant guide plates based on patient treatment conditions, and finally produces personalized high-precision metal implant guide plates through CAD/CAM rapid printing, which are applied in clinical practice.

### **2.3.3 Miniscrew design**

Miniscrews have become an important component in orthodontic treatment, providing a reliable source of anchorage for tooth movement. Research in this area has focused on developing new miniscrew designs to optimize their function and stability.

One research direction has been on investigating the effect of thread design on miniscrew stability. Studies have explored the impact of thread pitch, depth, and shape on the successful insertion and stability of miniscrews. Additionally, research has examined the use of self-drilling or self-tapping miniscrews, which eliminate the need for predrilling a pilot hole prior to insertion.

Another research focus has been on the use of surface treatments to improve miniscrew stability. Studies have investigated the impact of different surface treatments, such as acid etching, sandblasting, and anodizing, on the osseointegration and stability of miniscrews. Additionally, research has explored the use of biomaterial coatings, such as hydroxyapatite and titanium dioxide, to enhance the osseointegration of miniscrews.

Furthermore, researchers have explored the impact of miniscrew design on patient comfort and acceptance. Studies have investigated the use of miniscrews with different head designs, such as flat, square, or dome, to minimize tissue irritation and discomfort during treatment. Additionally, research has examined patient satisfaction with miniscrew design and ease of use.

## **2.4 Digital model**

There is currently no consensus on which technology is most accurate for modeling (Akyalcin et al.,2013;Flügge TV et al.,2013).Different modeling methods have their own advantages and disadvantages. The most commonly used digital 3D modeling methods in clinical practice include laser 3D scanning technology, CT scanning technology, and direct intraoral scanning technology.Akyalcin et al. established three digitalization models for 30 orthodontic patients and found that the deviation of laser scanning is the smallest and its accuracy is better than CBCT(Akyalcin et al.,2013). Kim et al. established laser scanning digital models, physical models, and CBCT digital models for 60 orthodontic patients and measured their tooth width, arch length, and width. They found that the accuracy of laser scanning digital models was high( Kim et al .,2014). Kim et al. measured the anterior and full tooth bolton ratios

of 50 patients and found that laser scanning had higher accuracy compared to CBCT(Kim et al.,2016).

## **2.5Computer-Aided Design and Manufacturing(CAD/CAM)**

Computer Aided Design (CAD) and Computer Aided Manufacturing (CAM) is becoming increasingly mature and plays a crucial role in stomatology.3D printing technology as a rapid prototyping technology that is a widely used technique in stomatology in the 20th century.The new industrial manufacturing technology developed in the late 1980s was initially used in industries such as aviation and aerospace.It refers to the use of materials such as photosensitive resins to layer computer-aided design models through design software.A technique of layer by layer stacking, editing and shaping contours to create a three-dimensional solid model. CAD/CAM technology is a means of transforming virtual designs into entities (Voss PJ ,et al., 2019).

## Chapter 3

### MATERIAL AND METHODS

#### 3.1 Study design

This is a Randomised control trial.

#### 3.2 Population and sample

##### 3.2.1 References population

Orthodontics patients which is require to implant miniscrew as anchorage requirement at the Department of Stomatology, Xuanwu Hospital of Traditional Chinese Medicine.

#### 3.3 Source of population

The samples will be recruited from the Dental Clinic, Beijing Xuanwu Traditional Chinese Medicine Hospital , Beijing Xuanwu TCM Hospital.

#### 3.4 Ethical Considerations

Ethical approval has been obtained from Beijing Xuan Wu Hospital of Traditional Chinese . This study will apply for ethical approval from the Human Research Ethics Committee of USM.

This clinical trial will also planned to register in Clinical trial.gov.my.

**Before collecting any personal data, ensure that all participants understand the purpose of data use and obtain their written consent.**

**All researchers will participate in data protection and privacy training to ensure they understand and comply with data protection policies. Establish a security incident reporting mechanism to ensure that any security incidents can be reported and handled in a timely manner.**

### **3.5 Sample size calculation**

Sample size were determined using power and sample size calculation software (version 3.1.9.7) (Dupont and Plummer 1990). Since the sample size calculated for other objectives gave less number of subjects in each group, therefore the sample size selected in this research is based on objective of miniscrew implantation. The given below are the categorization as per objective.

#### **3.5.1 Objective 1**

Sample size calculation based on the objective 1 related to the of guide on the miniscrew implantation. In a previous study the response within each subject group was normally distributed with standard deviation 1.82437mm([name],Song Hui and Xiaofeng Huang,2022). If the true difference in the experimental and control means is 2.7403, the research will need to study 8 experimental subjects and 8 control subjects to be able to reject the null hypothesis that the population means of the experimental and control groups are equal with probability (power) 0.8. The Type I

error probability associated with this test of this null hypothesis is 0.05. The effective size is 1.5451013.

### **3.5.2 Objective 2**

Sample size calculation based on the objective 1 related to the of guide on the miniscrew implantation. In a previous study the response within each subject group was normally distributed with success rate 86%, failure rate 2% (Lim H, et al.,2011). The research will need to study 8 experimental subjects and 8 control subjects to be able to reject the null hypothesis that the population means of the experimental and control groups are equal with probability (power) 0.8. The Type I error probability associated with this test of this null hypothesis is 0.05.

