### **3.5.3 Objective3**

Sample size calculation based on the objective 1 related to the of guide on the miniscrew implantation. In a previous study the response within each subject group was normally distributed with standard deviation 0.12mm(Janson G, et al.,2013). If the true difference in the experimental and control means is 0.66, the research will need to study 10 experimental subjects and 10 control subjects to be able to reject the null hypothesis that the population means of the experimental and control groups are equal with probability (power) 0.8. The Type I error probability associated with this test of this null hypothesis is 0.05. The effective size is 1.3929508.

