### **3.5.4 Objective 4**

Sample size calculation based on the objective 1 related to the of guide on the miniscrew implantation. In a previous study the response within each subject group was normally distributed with standard deviation 0.02 um(Talaat S., et al.,2017). If the true difference in the experimental and control means is 0.54, the research will need to study 6 experimental subjects and 6 control subjects to be able to reject the null hypothesis that the population means of the experimental and control groups are equal with probability (power) 0.8. The Type I error probability associated with this test of this null hypothesis is 0.05. The effective size is 1.799001.

Thus, a total sample size for this study will be 24 (12 for experimental and control group) after considering 20% drop-out.

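### Section 3.5 claims 80% power for every objective, but Objective 2's 8 per arm has no derivation and the SDs printed for Objectives 3 and 4 contradict their stated effect sizes

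*Protocol*

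**What the plan says.** Sections 3.5.1 to 3.5.4 each give a sample size for power 0.8 and type I error 0.05.

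- **Objective 1 (accuracy), 3.5.1:** SD 1.82437 mm, difference 2.7403, effect size 1.5451013, 8 per arm.
- **Objective 2 (stability), 3.5.2:** the response is described as "normally distributed with success rate 86%, failure rate 2" per cent. The text then states: "The research will need to study 8 experimental subjects and 8 control subjects to be able to reject the null hypothesis", and the hypothesis concerns equality of means. No SD, difference or effect size is given.
- **Objective 3 (safety), 3.5.3:** "normally distributed with standard deviation 0.12mm", difference 0.66, 10 per arm. "The effective size is 1.3929508".
- **Objective 4 (CBCT against digital model), 3.5.4:** "standard deviation 0.02 um", difference 0.54 without a unit, 6 per arm. "The effective size is 1.799001".

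The conclusion in 3.5.4 is "a total sample size for this study will be 24 (12 for experimental and control group) after considering 20% drop-out". The opening of 3.5 explains why the miniscrew implantation objective was used: "Since the sample size calculated for other objectives gave less number of subjects in each group". Sections 3.5.2 to 3.5.4 each begin by saying that the calculation is based on objective 1.

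**The concern.** Objective 2 applies the language of a continuous outcome to a success/failure outcome. Two rates that do not add to 100% and belong to no named arm do not define a contrast, so nothing in the text leads to 8 per arm. Stability is listed among the main efficacy indicators (3.13) and has its own alternative hypothesis (1.11.4). The 80% claim therefore tells readers that 24 patients can test it, and a non-significant result could be read as equal stability.

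For Objectives 3 and 4 the printed SD and difference do not give the printed effect size. Objective 3 has the largest requirement and is the only one that leads to 24, so the basis of the trial's size cannot be verified from the page. The opening of 3.5 points to a different objective from the one that produces the total.

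**Working it through.** All calculations are two-sided at alpha 0.05. The protocol does not state sidedness.

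**1. Effect sizes (difference divided by SD) and the n they give** (two-sample t-test, noncentral t)

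| Objective | Difference / SD | Stated effect size | SD implied by stated effect size | n per arm from stated effect size | Stated n |
|---|---|---|---|---|---|
| 1 | 2.7403 / 1.82437 = 1.502 | 1.545 | – | power 81.9% at 8 | 8 |
| 3 | 0.66 / 0.12 = 5.5 | 1.393 | 0.66 / 1.393 = 0.474 | 9.16, so 10 | 10 |
| 4 | 0.54 / 0.02 = 27 | 1.799 | 0.54 / 1.799 = 0.300 | 5.98, so 6 | 6 |

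The stated n for Objectives 3 and 4 follows from the stated effect sizes. The printed SDs do not fit: the ratios differ by factors of 5.5 / 1.393 = 3.9 and 27 / 1.799 = 15. Objective 4 assumes that both figures share a unit. Objective 1's gap is trivial: 1.502 still gives 79.8% power at 8 per arm.

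**2. Objective 2, attempts to reach 8 per arm at 80%**

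- Literal reading, 86% in one arm and 2% in the other: Fisher power at 8 per arm is 97.0%, not 80%. It also sets a success rate against a failure rate.
- 86% against its own complement, 14%: Fisher power is 68.9% at 7 and 82.4% at 8, so 8 would be the smallest n. But 14% is not in the text, conflicts with the printed 2%, and is not a comparison between arms.
- 86% success against 98% success (failure 14% against 2%), an assumed pairing: n = [1.96·√(2 × 0.92 × 0.08) + 0.8416·√(0.86 × 0.14 + 0.98 × 0.02)]² / 0.12² = (0.752 + 0.315)² / 0.0144 = 79.04, so 80 per arm. Fisher's test needs about 85 (power 0.801; at 80 it is 0.766).

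**3. Power for stability, one binary result per patient**

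| Success rates | n per arm | Fisher | Chi-square, uncorrected | Normal approximation |
|---|---|---|---|---|
| 86% v 98% | 8 | 0.2% | 1.5% | 13.5% |
| 86% v 98% | 12 | 1.4% | 5.9% | 18.4% |
| 86% v 100% | 12 | 1.8% | 7.5% | 26.1% |

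The last row can be checked by hand. With no failures among 12 in the better arm, 4 failures among 12 in the other give Fisher p = 2 × 495 / 10626 = 0.093, and 5 give 2 × 792 / 42504 = 0.037. At least 5 failures are therefore needed, and with a 14% failure rate the probability of that is 1.8%.

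Conversely, with 86% success in one arm, 80% power requires success in the other at or below about 15% (Fisher) to 26% (chi-square) at 8 per arm, or 27% to 35% at 12 per arm.

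**4. Which objective gives 24**

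Objective 1: 8 × 1.2 = 9.6, or 8 / 0.8 = 10 per arm. Objective 3: 10 × 1.2 = 12 per arm. Only Objective 3 gives 24, although 3.5 says the other objectives need fewer than the implantation objective.

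**5. Drop-out**

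To keep 10 per arm after 20% loss, 10 / 0.8 = 12.5, so 13. With 24 enrolled, 24 × 0.8 = 19.2, about 19 evaluable. At effect size 1.393, power is 81.5% with 10+9 and 79.2% with 9+9. The effect detectable with 80% power is 1.37 SD (10+9) or 1.41 SD (9+9).

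**The case against.** The strongest counter-argument concerns Objectives 3 and 4. If each effect size used the root mean square of two group SDs, then SDs of 0.53 and 0.41 give 0.66 / √((0.53² + 0.41²) / 2) = 1.39295, and 0.31 and 0.29 give 0.54 / √((0.31² + 0.29²) / 2) = 1.79900. Both match the stated values, and the differences between these SDs are 0.12 and 0.02, exactly the printed SDs. This is an inference, as none of the four SDs is in the protocol. If it is right, the differences, effect sizes and n are sound and the printed SDs are labelling slips. That supports calling the point misreporting. It does not rescue the printed SDs, which 3.5.3 and 3.5.4 say apply within each group.

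For Objective 2, the protocol never states 86% against 98% to 100%, so the shortfall depends on an assumed contrast. The outcome format is also open, since Annexure C tabulates stability by month. Both points stand as limits on the size of the shortfall. Neither supplies a derivation of 8 per arm.

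The contradiction over which objective sized the trial does not change the total, which follows the largest requirement. The drop-out slip is likewise minor, and 9+9 is a 25% loss, beyond the planned 20%.

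**Conclusion.** The concern holds. The 80% power claim for stability has no basis in its stated inputs. Assuming one binary result per patient, 86% success in one arm and a better result in the other, 24 patients cannot give that power even at 100% success: 1.8% by Fisher, 7.5% by chi-square and 26% by normal approximation. The SDs printed for Objectives 3 and 4 are inconsistent with the effect sizes by factors of 3.9 and 15, but the stated n values agree with the effect sizes, so no power shortfall is shown there. The statement that the other objectives need fewer subjects is contradicted by Objective 3. The drop-out slip is minor: at the planned 20% loss split 10+9, power at Objective 3's effect size stays above 80%.

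**What to change.** Keep 24 patients and revise section 3.5.

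1. Correct the SDs or effect sizes for Objectives 3 and 4, and the units in Objective 4, so that each difference and SD reproduce the stated effect size. If two group SDs were combined, print both and the formula.
2. Name the one objective and the one variable that size the trial. Correct the opening of 3.5 and the copied openings of 3.5.2 to 3.5.4 to match.
3. Delete the 80% power claim for Objective 2. Report stability as failure proportions per arm with an exact confidence interval, and state that it is not powered.
4. State that 24 enrolled with 20% loss leaves about 19 evaluable, with 80% power for about 1.37 SD (1.41 SD if 9+9).

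The cost is text and figures in 3.5, with perhaps a matching word in 1.11.4 and 3.13 on the status of stability. Enrolment, allocation and outcomes do not change. The stated power becomes less favourable, and stability can no longer be presented as a powered comparison.
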